## **7.0 STATISTICAL METHODS**

### **7.1 General Statistical Conventions**

All statistical procedures will be completed using SAS version 9.4 or higher.

Unless otherwise specified, all statistical hypothesis testing for the primary and secondary efficacy endpoints will be two-sided and will be performed using a significance (alpha) level of 0.05. Two-sided 95% confidence intervals (CI) will be provided when relevant.

For categorical variables, summaries will include counts of subjects (frequencies) and percentages. Percentages will be rounded to one decimal place.

For summary purposes, baseline will be defined as Visit 1, the screening visit value; all summaries will be presented by treatment group, unless otherwise specified.

### **7.2 Subject Disposition**

All subjects who provided informed consent will be included in a summary of subject accountability. The number of subjects screened, the number of screen failures, the number and percent of subjects randomized will be summarized.

Subject disposition information will be summarized by treatment group and overall. The number of subjects completing and withdrawing from the study will be tabulated in the study disposition table which will also include the primary reason for withdrawal of the subject as reported on the eCRF.

### **7.3 Demographics and Baseline Characteristics**

No formal comparison between treatment groups for demographic or baseline characteristics will be done.

### **7.3.1 Demographics**

Age and other continuous demographic variables at baseline will be summarized descriptively.

## **7.4 Efficacy Analyses**

This section addresses separately the analyses to be conducted on the primary, key secondary, and secondary efficacy variables. All definitions relative to efficacy endpoints are detailed in Section 4.0.

### **7.4.1 Analysis Methods**

#### **7.4.1.1 Analysis of Proportions Using Two-sided Z-test**

The proportion of subjects with ACC grade of 0 at a given time point in the ISV-305 (PISV) and vehicle (PVEH) groups will be compared using a two-sided Z-test with continuity correction and pooled variance.

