## **5.2 Modified Intent-To-Treat Population (mITT)**

The mITT population includes randomized subjects that undergo cataract surgery, receive at least one dose of IP, and have at least one post-surgery efficacy assessment. Subjects who receive rescue medications will be included in the mITT but will be treated as failures. This population will be used in all efficacy analyses. Subjects in the mITT population will be analyzed in the treatment group to which they were assigned by the randomization scheme, regardless of which IP if any, they receive.

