### 6.1.1 Definitions Relative to Efficacy Parameters

#### **Proportion of Subjects with ACC Grade 0 at a Given Time Point**

Proportion = Number of responders at Day X / Total number of subjects in the mITT population

Notes:

1. Responders are those subjects who had ACC grade of 0 either at Day X or the last assessment prior to Day X visit (in case the Day X was not completed).
2. Those subjects who received a rescue medication between and including Day 0 and X will be considered as treatment failure or non-responder, despite a subject with zero cell count either at Day X or the last assessment prior to Day X visit (in case the Day X was not completed).

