#### **7.4.1.2 Multiplicity**

Multiplicity adjustments will control the overall type I error rate at 0.05 for testing two treatment groups and multiple endpoints.

Among the primary and key secondary endpoints, the tests will be performed using a serial gatekeeping procedure based on the hierarchical order of the primary and key secondary endpoints. Therefore, the statistical tests on the key secondary endpoints across all five postsurgical time points will only be performed in case the null hypothesis for the primary endpoint is rejected.

The following multiplicity adjustment will be used to strongly control the overall type I error rate at 0.05 for the key secondary endpoints at each assessment. Multiplicity will be addressed via Hochberg's step-up method.

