### **7.4.2 Analysis of Primary Efficacy Endpoint**

The primary efficacy endpoint is the proportion of subjects with an ACC grade of 0 at Day 15.

The difference between treatment groups will be tested using a two-sided Z-Test with continuity correction and pooled variance using the mITT population. A subject with an ACC grade of 0 at the Day 15 visit or the last assessment prior to the Day 15 visit (in the event that Day 15 was not completed) will be considered a responder to therapy. If a subject has an ACC score of >0 at Day 15 or the last assessment prior to the Day 15 visit (in the event that Day 15 was not completed), that subject will be considered a failure (or non-responder) in the primary efficacy endpoint analysis. Additionally, any subject receiving a rescue medication between Day 0 and the Day 15 visit (inclusive) will be considered a treatment failure.

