### 7.4.3 Analysis of Key Secondary Efficacy Endpoints

If the null hypothesis for the primary endpoint is rejected, the statistical tests on the key secondary endpoints across all five post-surgical time points will be performed using the serial gatekeeping procedure known as Hochberg's step-up method.

For the key secondary efficacy endpoint of proportion of subjects who achieve a pain score of 0 on the VAS, the difference between the treatment groups at each post-surgical assessment will be tested using a two-sided Z-Test with continuity correction and pooled variance. Missing values will be imputed using the LOCF method. Hochberg's method will be applied to the ordered p-values from these tests across the five time points. A 95% CI for the difference of the proportions at each time point will also be constructed. The effect of imputing missing values for this secondary endpoint analysis of proportions using the LOCF method will be assessed via a multiple imputations procedure.

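### The continuity-corrected Z-test holds 5% but uses only about 2.7–4.0% of it at 160/80 (null rates 10–90%); an unconditional exact test recovers most of the rest at no cost in subjects

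*SAP*

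**What the plan says.** SAP 7.4.1.1 states that the two response proportions "will be compared using a two-sided Z-test with continuity correction and pooled variance". SAP 7.4.2 applies this to the primary endpoint (at Day 15, the share of subjects graded 0 for ACC) in these words: "The difference between treatment groups will be tested using a two-sided Z-Test with continuity correction and pooled variance using the mITT population". SAP 7.4.3 applies it to VAS pain of 0 at Days 1, 8, 15, 18 and 29: "the difference between the treatment groups at each post-surgical assessment will be tested using a two-sided Z-Test with continuity correction and pooled variance". For those five tests, Hochberg's "method will be applied to the ordered p-values from these tests across the five time points", and only if the primary null hypothesis is rejected.

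On error rates, SAP 7.1 says that testing "will be two-sided and will be performed using a significance (alpha) level of 0.05", and SAP 7.4.1.2 that "Multiplicity adjustments will control the overall type I error rate at 0.05". The estimate is a crude proportion with the whole mITT arm as denominator (SAP 6.1.1: "Proportion = Number of responders at Day X / Total number of subjects in the mITT population"). Planned arms are 160 and 80 (Protocol 2.0, SAP 3.1). The mITT set can be smaller, because subjects must have surgery, "receive at least one dose of IP, and have at least one post-surgery efficacy assessment" (SAP 5.2).

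The supplied text gives no reason for the correction, no expected response rates and no sample-size calculation.

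**The concern.** A continuity correction pulls the statistic towards zero. With arms of this size it can push the true type I error well below the nominal level, so power is given up without any gain in validity beyond what a test with guaranteed size already offers.

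The primary test carries the most weight because it is the gate for all five pain tests: a narrow miss there means no pain comparison is tested at all. The same conservatism recurs inside the Hochberg step, where the individual levels are smaller.

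**Working it through.** **Inputs.** Arms of 160 and 80, two-sided alpha 0.05, and the corrected pooled Z all come from the documents. Response rates are assumptions, because none are stated. Arm sizes of 152/76 stand for an assumed 5% loss from randomisation to mITT. There is no stated power or size figure to reproduce.

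**Planned statistic.** With x₁/n₁ and x₂/n₂ the observed proportions and p̄ the pooled proportion,

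Zc = (|x₁/n₁ − x₂/n₂| − ½(1/n₁ + 1/n₂)) / √[p̄(1 − p̄)(1/n₁ + 1/n₂)], rejecting when Zc ≥ 1.96.

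At 160/80 the correction is ½(1/160 + 1/80) = 0.009375, or 0.94 percentage points off the observed difference.

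**Size.** The null probability of rejection was summed over all 161 × 81 = 13,041 outcomes of two independent binomials with a common rate. The exact test takes the smallest cut-off on the uncorrected pooled Z whose maximum size, over null rates of 0.1–99.9% in 0.1-point steps, does not exceed 5%.

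| Arms | Planned size, null rates 10–90% | Uncorrected Z, maximum | Exact cut-off | Exact size, maximum | Extra rejections | Lost rejections |
|---|---|---|---|---|---|---|
| 160/80 | 2.67–3.98% | 5.10% | 1.971 | 4.95% | 206 | 0 |
| 152/76 | 2.60–3.60% | 5.47% | 1.980 | 4.91% | 204 | 0 |

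Outside 10–90% the planned test is more conservative still: at 160/80 its size is 1.9% at a null rate of 5% or 95%, and 0.7% at 2% or 98%.

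**Other arm sizes.** Over 121 pairs (active 140–160 in steps of 2, vehicle 70–80) the exact test rejects every outcome the planned test rejects. Its maximum size is 4.74–5.00% and its cut-off 1.962–2.005, while the uncorrected test's maximum is 5.05–5.70%. A separate check of 19 pairs from 120/60 to 165/82 also found no lost rejection.

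**Hochberg levels at 160/80.** The five levels are 0.05/k for k = 1 to 5; the first is in the table above.

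| Level | Planned size, null rates 10–90% | Exact size, maximum |
|---|---|---|
| 2.5% | 1.31–1.81% | 2.43% |
| 1.67% | 0.81–1.19% | 1.66% |
| 1.25% | 0.60–0.91% | 1.22% |
| 1% | 0.46–0.69% | 0.99% |

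No planned rejection is lost at any of the five levels at 160/80, 152/76, 150/78 or 155/73. At those sizes, Hochberg with exact p-values therefore rejects everything the planned version rejects.

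**Power at 160/80, assumed rates.**

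| Vehicle vs active | Planned | Exact |
|---|---|---|
| 10 vs 25% | 76.9% | 81.7% |
| 30 vs 45% | 56.2% | 60.9% |
| 30 vs 50% | 82.1% | 84.6% |
| 50 vs 70% | 82.2% | 85.4% |
| 30 vs 55% | 95.3% | 96.2% |
| 30 vs 60% | 99.3% | 99.4% |

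Gain in percentage points, over vehicle rates from 10% up to an active rate of 90%:

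| Difference | 160/80 | 152/76 |
|---|---|---|
| 15 points | 3.6–5.6 | 4.0–6.2 |
| 20 points | 1.5–3.3 | 1.8–4.0 |
| 25 points | 0.25–1.15 | 0.35–1.6 |
| 30 points | at most 0.23 | at most 0.38 |

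To match the exact test at 240 subjects, the planned test needs about 258 at 30 vs 50%, 264 at 30 vs 45% and 267 at 10 vs 25%, that is 18, 24 and 27 more. For a single test at the 1% level, 30 vs 50%, power is 60.1% planned and 64.9% exact.

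**Worked outcomes at 160/80.**
- 70/160 vs 24/80: the difference is 0.1375, p̄ = 94/240 and the SE is 0.0668. Zc = (0.1375 − 0.009375)/0.0668 = 1.917, p = 0.055. Uncorrected Z = 2.057, above 1.971; exact p = 0.041.
- 102/160 vs 40/80: planned p = 0.057, exact p = 0.042.
- 69/160 vs 24/80: uncorrected Z = 1.967, p = 0.049, but exact p = 0.0505. Here dropping the correction would reject and the exact test would not.

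**The case against.** The strongest reply is that nothing is broken. The SAP names one standard, reproducible test that keeps its promise on type I error, and erring towards conservatism is defensible for a Phase 3 primary endpoint. That stands, and it is why this is a suggestion and not a correction.

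The benefit also cannot be established from the documents. They give no rates, and 240 subjects may have been sized with the correction in mind, in which case the change only adds margin. For a true difference of 30 points the margin is negligible. The tests disagree on only 206 of 13,041 outcomes (1.6%), and the worked examples come from that borderline set. This too stands as a limit on size. It is not a reason to keep the planned test, since the unused alpha is recoverable either way.

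Two further limits hold. Containment is a numerical finding at the sizes checked, not a theorem. The effect through the gate has not been quantified as joint power, and the 1% comparison is Hochberg's least favourable step.

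**Conclusion.** The concern holds as an optional efficiency improvement. At 160/80 the planned test spends 2.7–4.0% of the allowed 5% for null rates of 10–90%, and less outside that range. An unconditional exact test on the same crude proportions and the same subjects stays within 5% and kept every planned rejection at all arm sizes checked. For assumed differences of 15–20 points it gains about 1.5–5.6 percentage points of power at 160/80; for 30 points or more the gain is negligible. These figures treat responders as independent binomials and take the LOCF rule and the mITT definition as given.

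**What to change.** Before unmasking, replace the corrected Z-test in SAP 7.4.1.1, 7.4.2 and 7.4.3 with a two-sided unconditional exact test ordered on the uncorrected pooled Z. The p-value is the maximum, over the common null rate, of the probability of a pooled Z at least as large as the one observed. Specify it as a procedure, with the null-rate grid stated, and compute it at the final mITT arm sizes, because the cut-off depends on them. Feed the p-values into the existing gate and Hochberg step. Keep the crude mITT difference as the estimate. Do not merely delete the correction.

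The cost is SAP wording and a short program, with no extra subjects. Two details need settling at the same time:

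- SAP 7.4.3 names no method for its 95% CI. Name one alongside the test, since test and interval can disagree near 0.05.
- The exact test does not pool directly over imputed data sets, so the multiple-imputation check in 7.4.3 should keep an analysis based on an estimate and its standard error.

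A site-stratified CMH test could be added as a sensitivity analysis only. Any gain from it depends on site variation and within-site balance that the documents do not give.

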#### **7.4.1.2 Multiplicity**

Multiplicity adjustments will control the overall type I error rate at 0.05 for testing two treatment groups and multiple endpoints.

Among the primary and key secondary endpoints, the tests will be performed using a serial gatekeeping procedure based on the hierarchical order of the primary and key secondary endpoints. Therefore, the statistical tests on the key secondary endpoints across all five postsurgical time points will only be performed in case the null hypothesis for the primary endpoint is rejected.

The following multiplicity adjustment will be used to strongly control the overall type I error rate at 0.05 for the key secondary endpoints at each assessment. Multiplicity will be addressed via Hochberg's step-up method.

### **7.4.2 Analysis of Primary Efficacy Endpoint**

The primary efficacy endpoint is the proportion of subjects with an ACC grade of 0 at Day 15.

The difference between treatment groups will be tested using a two-sided Z-Test with continuity correction and pooled variance using the mITT population. A subject with an ACC grade of 0 at the Day 15 visit or the last assessment prior to the Day 15 visit (in the event that Day 15 was not completed) will be considered a responder to therapy. If a subject has an ACC score of >0 at Day 15 or the last assessment prior to the Day 15 visit (in the event that Day 15 was not completed), that subject will be considered a failure (or non-responder) in the primary efficacy endpoint analysis. Additionally, any subject receiving a rescue medication between Day 0 and the Day 15 visit (inclusive) will be considered a treatment failure.

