3.2 Exclusion Criteria

The following are exclusion criteria for prospective study subjects to be confirmed at Visit 1 (Day -14 – Day -2) prior to randomization. The sponsor will not grant any protocol eligibility waivers.

- a. Have a history of Fuchs' dystrophy in the study eye
- b. Have a history of diabetic retinopathy (with visual impairment) and/or previous vitrectomy in the study eye within the last 2 years
- c. Have any sign of iritis or scleritis in the study eye

- d. Have a history of glaucoma surgery in the study eye within the last 2 years
- e. Have an existing diagnosis of severe dry eye in the study eye
- f. Have known hypersensitivity or poor tolerance to any component of the IP or any of the procedural medications such as anesthetic and/or fluorescein drops, dilating drops, etc.
- g. Have an acute ocular infection (bacterial, viral or fungal) or active ocular inflammation in the study eye
- h. Have any extraocular/intraocular inflammation in the study eye noted prior to surgery (blepharitis is allowed if scurf only without any concurrent conjunctivitis or lid erythema/edema) or ongoing, unresolved uveitis
- i. Use of the following disallowed medications within a specified amount of time before surgery:
 - topical, inhaled, or oral corticosteroids within 15 days
 - depot-corticosteroids within 45 days (triamcinolone within 90 days)
 - topical, systemic, or inhaled nonsteroidal anti-inflammatory drugs (NSAIDs) within 1 week (with the exception of low-dose aspirin)
 - ocular or systemic antihistamines, or mast cell stabilizers within 1 week
 - other analgesics and use of acetaminophen (Tylenol[®]) within 48 hours
 - any medication that the investigator feels may interfere with the study parameters
- j. Have any active or chronic/recurrent ocular or systemic disease that is uncontrolled and likely to affect wound healing (e.g., diabetes mellitus, systemic connective tissue disease, severe atopic disease)
- k. Have known blood dyscrasia or bone marrow suppression
- l. Have any active corneal pathology noted in the study eye
- m. Have any intraocular inflammation (cells or flare in anterior chamber) or ocular pain (greater than 0) on the pain scale in either eye
- n. Have had radial keratotomy, corneal transplant, or LASIK in the study eye within the last 2 years
- o. Be currently pregnant, nursing, or planning a pregnancy, or be a woman that has a positive pregnancy test
- p. Are currently suffering from alcohol and/or drug abuse

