## 5.0 ANALYSIS POPULATIONS

All efficacy endpoints will be analyzed using the modified intent-to-treat (mITT) population. The Per-Protocol (PP) population will be used for the analysis of the primary and secondary endpoints to examine the robustness of the primary analyses.

Safety and tolerability will be analyzed using the safety population.

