## **6.2 Handling of Missing Data and/or Invalid Data and Outliers**

### **6.2.1 Missing Data Analysis Methods for Efficacy Data**

The Last Observation Carried Forward (LOCF) method will be used to impute missing values for the primary and all secondary endpoints. In LOCF imputation, missing Day X values will be imputed using the last non-missing observation prior to Day X.

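### LOCF is not restricted to post-surgery values, and the primary endpoint has no planned analysis under any other missing-data assumption

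*SAP*

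**What the plan says.** The carry-forward rule appears three times. SAP 6.2.1, which covers the primary and all secondary endpoints, says "missing Day X values will be imputed using the last non-missing observation prior to Day X". SAP 6.1.1 says "Responders are those subjects who had ACC grade of 0 either at Day X or the last assessment prior to Day X visit". SAP 7.4.2 repeats this for Day 15: "A subject with an ACC grade of 0 at the Day 15 visit or the last assessment prior to the Day 15 visit" counts as a responder if Day 15 was not completed. A last value above 0 makes the subject a failure, and so does rescue from Day 0 up to the Day 15 visit.

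Slit lamp and VAS are both done at Visit 1 (Protocol 6.1, Table 1), before surgery. Exclusion criterion m in Protocol 3.2 bars subjects who "Have any intraocular inflammation (cells or flare in anterior chamber) or ocular pain (greater than 0) on the pain scale in either eye".

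The mITT population (SAP 5.2) needs surgery, one dose and one efficacy assessment of any kind after surgery. That assessment need not be of the measure being analysed, nor fall before the time point being analysed.

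SAP 7.4.3 plans one check of LOCF, for VAS pain: the "effect of imputing missing values for this secondary endpoint analysis of proportions using the LOCF method will be assessed via a multiple imputations procedure". SAP 7.4.1.2 makes the pain tests conditional on the primary: they "will only be performed in case the null hypothesis for the primary endpoint is rejected".

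**The concern.** There are two separate problems.

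**Which values may be carried.** Before surgery there is no surgical inflammation or pain to treat, and subjects are selected for having none. A screening value carried across the operation is therefore a success by selection and says nothing about treatment. At Day 1 no earlier post-surgery VAS is scheduled, so LOCF as written can only reach back to screening. Day 1 pain is one of the five comparisons tested under Hochberg's method.

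**No second assumption for the primary.** The SAP accepts that LOCF needs checking, but plans the check only for the secondary endpoint. Some missing Day 15 grades should be expected, because under Protocol 2.0 stopping the product for any reason means withdrawal. LOCF can err either way: it credits an early grade 0 that might not have lasted, and it counts an early grade above 0 against a subject who might have cleared by Day 15. An analysis of how far the primary result depends on this is credible only if it is written before unmasking.

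**Working it through.** **Step 1. Which value fills the gap.**

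| Missing value | Earlier scheduled values of the same measure | Filled from | Likely result |
|---|---|---|---|
| Day 1 VAS pain | Visit 1 only | Screening | Success, if screening VAS was 0 |
| Day 15 ACC | Visit 1, Day 1, Day 8, any early-exit exam | Latest available | Screening used only if all later ones are missing |

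In the first row, a subject who misses Day 1 but is seen at Day 8 is in mITT and is filled from before surgery. The VAS is the only pain measure scheduled at Visit 1, so the pain scale in criterion m is most naturally the VAS, but the criterion does not name it. A screening score of 0 is expected, not explicitly required.

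In the second row, the subject must have no ACC grade after surgery up to Day 15 and still be in mITT. Slit lamp and VAS are scheduled at the same visits, and early exits should have the Visit 7 assessments, so this should be rare.

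**Step 2. How many reclassifications matter.** The documents supplied give no power, response rate or dropout figure to reproduce. They give about 240 subjects at 2:1 (160 and 80; Protocol 2.0), two-sided alpha 0.05 (SAP 7.1) and the pooled, continuity-corrected Z-test (SAP 7.4.2). The responder counts below are assumptions.

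Z = (|p1 − p2| − c) / √[p̄(1 − p̄)(1/160 + 1/80)], with c = 0.5 × (1/160 + 1/80) = 0.009375.

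- 60/160 vs 20/80: p̄ = 80/240 = 0.3333; Z = (0.125 − 0.009375)/0.06455 = 1.791; p = 0.073.
- 62/160 vs 20/80: p̄ = 82/240 = 0.3417; Z = (0.1375 − 0.009375)/0.06494 = 1.973; p = 0.0485.
- 72/160 vs 20/80: p̄ = 92/240 = 0.3833; Z = (0.200 − 0.009375)/0.06658 = 2.863; p = 0.004. Removing ten ISV-305 responders gives 62 vs 20, p = 0.0485; removing eleven gives 61 vs 20, p = 0.060.

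Two net reclassifications can decide a borderline result. A clear result withstands ten.

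**Step 3. Effect on the false-positive rate.** This is the exact binomial probability that the SAP test favours ISV-305 when both true rates are equal (nominal one-sided level 2.5%). The stated number of subjects is fixed as responders.

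| Assumed true rate, both arms | Fixed responders, ISV-305 / vehicle | Chance of a false ISV-305 win |
|---|---|---|
| 25% | 0 / 0 | 1.6% |
| 25% | 2 / 0 | 2.3% |
| 20% | 0 / 0 | 1.5% |
| 20% | 8 / 4 | 0.9% |
| 20% | 4 / 0 | 3.3% |
| 20% | 8 / 0 | 6.6% |

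Equal proportions credited in both arms do not inflate the rate. Two subjects credited in one arm only stay within the nominal level; four or eight do not. Nothing in the documents says how many there will be, or in which arm.

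**The case against.** The strongest case against has four parts.

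- **Screening values hardly reach the primary.** This stands, and it limits the first problem mainly to Day 1 pain.
- **The intended reading may already be post-surgery.** SAP 7.4.2 speaks of response to therapy, Visit 1 is defined separately as baseline, and mITT requires an assessment after surgery. These hints make the intention plausible, but none changes the rule, and a programmer working from SAP 6.2.1 would carry the screening value.
- **Day 1 pain already has multiple imputation.** True, but that is a check beside the main analysis. The p-values entering Hochberg's procedure still come from LOCF.
- **The primary has other protection.** Rescued subjects are failures whatever value is carried, which covers an obvious form of informative dropout. SAP 5.0 adds: "The Per-Protocol (PP) population will be used for the analysis of the primary and secondary endpoints to examine the robustness of the primary analyses". SAP 7.2 adds: "The number of subjects completing and withdrawing from the study will be tabulated in the study disposition table", with reasons and by arm. These help, but the per-protocol repeat changes who is analysed rather than how gaps are filled. The disposition table can reveal unequal withdrawal, but it is not stated to count carried-forward grades and it tests no other assumption. The separate document of table templates may add displays; it is not available here.

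A reader might infer that the plan is biased towards ISV-305 or inflates the type I error. The documents do not support that. They give no missingness by arm, LOCF can err in either direction, and Step 3 shows inflation only when several credits fall in one arm.

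**Conclusion.** Both parts hold as statements about the SAP text and should be fixed before unmasking. First, the carry-forward rule as written can turn a missing Day 1 VAS into a pain success using a value from before surgery, and in rare cases can do the same for ACC at Day 15. Second, the primary endpoint has no planned analysis under another missing-data assumption, although the secondary endpoint that depends on it has one.

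The direction and size of any bias cannot be stated. The figures above show only that the point could decide a borderline primary result and would not overturn a clear one. The Day 1 conclusion assumes that screening VAS scores are in fact 0.

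**What to change.** LOCF from post-surgery values stays the main rule.

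**(a) Carry-forward rule.** In SAP 6.1.1, 6.2.1, 7.4.2 and 7.4.3 state: *Only values of the same measure recorded after surgery are carried forward. An mITT subject with no such value at or before the time point is a non-responder in the main analysis.* In 7.4.3 also state that the multiple-imputation check covers both the carried-forward values and those set to non-response. Otherwise 7.4.3 would conflict with the new rule.

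**(b) Sensitivity analysis of the primary.** In SAP 7.4.2 add a descriptive tipping-point table in mITT:

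- Rows and columns give the number of ISV-305 and vehicle subjects without an observed Day 15 ACC grade who are counted as responders, from none to all.
- Subjects counted as failures because of rescue stay failures.
- Each cell shows both rates, the difference and the p-value from the primary test. The LOCF cell and the all-non-responder cell are marked.
- The number and source visit of carried-forward Day 15 ACC grades are reported by arm.

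The table does not alter the testing hierarchy. It should be read by how plausible the assumptions are where p crosses 0.05, not by counting cells, since the extreme corners are implausible.

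**Cost.** One SAP amendment and a little more analysis work; no change to the protocol, visits or sample size. Part (a) changes a main derivation, may lower response rates slightly (mainly Day 1 pain), and is not always conservative. Take an assumed Day 1 pain result under literal LOCF of 64/160 vs 20/80 (p = 0.031 before Hochberg). If three ISV-305 successes came from screening, the new rule gives 61/160 vs 20/80 (p = 0.060). If two vehicle successes did as well, it gives 61/160 vs 18/80 (p = 0.0225).
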